# **Efficacy and Safety of Sapylin Versus Dexamethasone Atomized Inhalation for Concurrent Chemoradiotherapy-Induced Oral Mucositis in Patients With Nasopharyngeal Carcinoma: A Randomized, Parallel, Non-inferiority Clinical Trial**

## **I. Rationale**

### **1. Background**

Nasopharyngeal carcinoma (NPC), an epithelial malignancy originating from the nasopharyngeal mucosa, is one of the common head and neck malignancies. Globally, 70% of new cases occur in East and Southeast Asia. Nearly 80% of global patients are concentrated in China, leading to its nickname, "China Cancer". Within China, it is highly prevalent in the southern regions, especially the Guangdong, Guangxi areas and Hong Kong, hence the common name "Guangdong Cancer". Currently, radiotherapy is the primary treatment modality for NPC. Seventy percent of patients are diagnosed at an advanced stage. For Locally Advanced NPC (LA-NPC), induction chemotherapy combined with Concurrent Chemoradiotherapy (CCRT) is the standard treatment regimen. Since the adoption of induction chemotherapy combined with CCRT for LA-NPC patients, overall survival rates have improved. However, over 20% of LA-NPC patients still experience treatment failure and have a 5-year survival rate lower than 5 years. Furthermore, during radiotherapy, the radiation causes varying degrees of damage to the normal tissues adjacent to the tumor. Adverse reactions such as dry mouth and radiation-induced oral mucositis can reduce patient compliance. In severe cases, these can lead to clinical adverse outcomes such as reduced radiation dosage, treatment interruption, prolonged hospitalization, or even life-threatening situations, thereby negatively impacting the efficacy and quality of life associated with CCRT. The INT0099 trial showed that 37% of patients receiving CCRT terminated treatment prematurely due to excessive toxicity.

Among radiation-induced adverse reactions, radiation-induced oral mucositis (RIOM) occurs in over 80% of patients undergoing radiotherapy. More than 50% of these patients even develop Grade 3-4 RIOM. Current clinical strategies for the prevention and treatment of RIOM include oral care, gargling medications, nebulized inhalation drugs, and local application of epidermal growth factor. Nebulized drug therapy has become an important method in cancer supportive care due to its ability to increase local drug concentration, decrease blood drug concentration, and achieve better compliance. MASCC/ISOO, ESMO, and other authoritative guidelines agree that there is currently no specific drug for the prevention and treatment of RIOM. Treatment focuses primarily on symptom relief and reducing complications. Epidermal Growth Factor (EGF) and corticosteroids are recommended. However, the long-term use of corticosteroids increases the risk of fungal infection and tends to cause radiotherapy interruptions. There is an urgent need for a highly effective and low-toxicity drug to prevent and treat RIOM. Zhao Weiwei and Chai Xieli, among others, concluded from relevant domestic and international studies that nebulized

inhalation therapy is a non-invasive, highly efficient, and low-side-effect approach in oncology treatment. However, the application of nebulized Sapylin is currently only reported in lung cancer, and its nebulized use in CCRT for NPC is rarely reported. Therefore, nebulized drug therapy for RIOM is one of the current research trends. Nishii et al. found that local application of corticosteroids can relieve edema, inhibit inflammation, and alleviate patient symptoms. Systemic use of corticosteroids tends to reduce radiotherapy interruptions but does not decrease the incidence or severity of RIOM. However, long-term local use of corticosteroids increases the risk of oral fungal infections. Nebulized traditional Chinese medicines lack multi-center clinical trials to evaluate their efficacy, thus limiting their application in NPC patients. However, a safer and more effective strategy is currently unavailable. Therefore, finding a drug with high efficacy and low side effects to improve RIOM in NPC patients and, consequently, enhance CCRT efficacy is crucial.

Sapylin (Group A streptococcus) is a Biological Response Modifier (BRM) with antitumor immune effects. Its main component is a lyophilized product of Group A streptococcus treated with penicillin. It effectively inhibits cancer cell proliferation, significantly enhances immune function, and increases the activity of various immune cells. It is widely used clinically to boost the immunity of cancer patients. In recent years, Sapylin has been used as an immune adjuvant in various cancers, such as lung cancer, breast cancer, gastric cancer, and bladder cancer. It has been shown to promote wound healing, enhance the efficacy of chemotherapy, and inhibit tumor cell proliferation. However, its role in tumor radiotherapy and its application in NPC patients are rarely reported. Sapylin (OK-432) is considered an adjuvant in cancer immunotherapy and has proven non-specific immune anti-tumor function. Additionally, Sapylin is believed to improve pleural fluid osmotic pressure and effectively reduce pleural effusion in some benign pulmonary diseases. To evaluate the effect of Sapylin on surgical treatment and immune function regulation in patients with thoracic malignancies, Tian et al. investigated the clinical data of 71 patients who received Sapylin in the surgical area shortly after surgery. Local intraoperative application of Sapylin (OK-432) was found to enhance early postoperative immune function in patients with thoracic malignancies, promote postoperative recovery, and improve prognosis. This implies it can reduce postoperative chest drainage, shorten intubation and hospital stay, and decrease patient suffering. The conventional routes of Sapylin (OK-432) administration are intramuscular and subcutaneous injection, which can cause injection site pain and fever. Nebulized inhalation of Sapylin is non-invasive, highly efficient, and has low side effects. Moreover, it can exert its effects in improving RIOM and its antitumor activity by enhancing cellular immunity. This approach may be a safe and effective method for LA-NPC patients receiving induction chemotherapy combined with CCRT. This study is the first prospective, randomized controlled trial to evaluate the incidence rate, severity, efficacy, and survival analysis of RIOM in NPC patients receiving CCRT combined with nebulized Sapylin versus CCRT combined with nebulized Dexamethasone. It aims to provide innovative research evidence for the correct use of Sapylin in LA-NPC patients. This study provides scientific evidence for a prospective randomized investigation into whether nebulized Sapylin can reduce the incidence and severity of RIOM in LA-NPC patients.

## 2. Current Status of Domestic and International Research

### (1) Current status of concurrent chemoradiotherapy for locally advanced NPC

Studies over the past 20 years indicate that concurrent chemoradiotherapy (CCRT) plays a crucial role in the treatment of LA-NPC. Both clinical studies and meta-analyses have confirmed that induction chemotherapy combined with CCRT offers significant survival benefits compared to radiotherapy alone, especially for patients with locally advanced disease. A Phase III clinical study enrolled 284 patients with Stage III and IV NPC without distant metastasis, randomly assigning them to a radiotherapy-alone group or an induction chemotherapy combined with CCRT group. The results showed that the locoregional failure rate and distant metastasis rate in the CCRT group were significantly lower than those in the radiotherapy-alone group. Furthermore, the 5-year nasopharyngeal failure-free survival rate (89.3%), failure-free survival rate (71.6%), and overall survival rate (72.3%) in the induction chemotherapy combined with CCRT group were significantly higher than those in the latter, with only a mild increase in Grade 3/4 acute toxicities. A Phase III clinical study conducted by Chan et al. reached similar conclusions, showing that the 5-year OS of the concurrent group was significantly higher than that of the radiotherapy-alone group, with a hazard ratio for death of 0.71, which further decreased to 0.51 in the T3-4 subgroup analysis. A meta-analysis comparing induction chemotherapy combined with CCRT versus radiotherapy alone (including a total of 1608 patients) showed that the relative risks (RRs) for death at 2, 3, and 5 years in the induction chemotherapy combined with CCRT group were [0.63, 95% CI (0.50–0.80)], [0.76, 95% CI (0.61–0.93)], and [0.74, 95% CI (0.62–0.89)], respectively. Currently, induction chemotherapy combined with CCRT has become the standard treatment model for LA-NPC. The latest NCCN guidelines recommend induction chemotherapy combined with CCRT as one of the standard treatment regimens for LA-NPC. However, studies have shown that CCRT is associated with higher toxicity compared to radiotherapy alone, and these toxicities can reduce patient compliance and treatment efficacy. Liu et al. comprehensively analyzed 2605 patients across 8 studies and found that in the era of Intensity-Modulated Radiation Therapy (IMRT), the efficacy of induction chemotherapy combined with CCRT was comparable to that of induction chemotherapy combined with radiotherapy alone, but induction chemotherapy combined with CCRT had a higher incidence of Grade 3/4 toxicities during radiotherapy. Therefore, in the IMRT era, induction chemotherapy combined with CCRT might be replaced by new treatment mode combinations. Currently, several ongoing prospective randomized clinical studies are comparing the efficacy of induction chemotherapy combined with CCRT against other comprehensive treatment modes that do not utilize induction chemotherapy combined with CCRT under the premise of using IMRT technology, and the results are eagerly anticipated. Additionally, radiation-induced toxicity remains one of the primary reasons affecting the therapeutic efficacy and quality of life of LA-NPC patients; reducing the incidence and severity of toxicity has become an urgent topic in current research.

## **(2) Research progress on the treatment of radiation-induced oral mucositis**

Due to the high incidence and pathogenesis of RIOM, the Mucositis Study Group of the Multinational Association of Supportive Care in Cancer/International Society of Oral Oncology (MASCC/ISOO) released updated clinical practice guidelines for mucositis in 2020. Subsequently, ESMO also updated its guidelines for the prevention and treatment of RIOM. In China, the Radiation Oncology Branch of the Chinese Medical Association released the Expert Consensus on Prevention and Treatment Strategies for Radiation-Induced Oral Mucositis in 2019. Clinical practice guidelines and expert consensus believe that: prevention is the priority

for RIOM, with good oral hygiene environment and care being the primary preventive measures; there is currently no specific drug for the prevention and treatment of RIOM, and treatment mainly lies in alleviating symptoms and reducing the occurrence of complications. Nutrition support, pain control, and the prevention and treatment of secondary infections are considered the cornerstones of RIOM management. The guidelines and consensus list drugs currently used domestically and internationally for the prevention and treatment of RIOM, such as analgesics, Epidermal Growth Factor (EGF), corticosteroids, Amifostine, and Leucogen, but analgesics have drawbacks such as short duration of action and significant side effects. Nishii et al. found that local use of corticosteroids can reduce edema, inhibit inflammatory responses, and alleviate patient symptoms, but long-term use increases the risk of oral fungal infections; while systemic use of corticosteroids has a trend of reducing radiotherapy interruptions, it does not reduce the incidence and severity of RIOM. Nicolatou-Galitis et al. found that when Amifostine is administered intravenously, there are side effects such as hypotension, nausea, and infusion-related reactions, whereas subcutaneous injection 60 minutes before radiotherapy in head and neck cancer patients, although significantly reducing side effects, lowers efficacy and compliance. Furthermore, due to inconsistent conclusions across studies and insufficient evidence levels, the guidelines and consensus do not yet recommend recombinant human granulocyte-macrophage colony-stimulating factor (GM-CSF), glutamine, and supersaturated calcium phosphate mouthwashes for the prevention of RIOM, nor do they recommend the local prophylactic use of antibiotics and hormones.

Therefore, the Chinese expert consensus on prevention and treatment strategies for radiation-induced oral mucositis believes that although much research has been conducted on the prevention and treatment of RIOM, many prevention and treatment strategies remain controversial due to the lack of large-scale multicenter randomized controlled trials. It looks forward to carrying out big data analysis of multicenter symptom management, with a view to discovering more complete risk factors for RIOM and finding safer and more effective prevention and treatment strategies, thereby improving the efficacy of concurrent chemoradiotherapy in patients with NPC.

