## **2. Research Goals and Content**

### **2.1 Research Goals**

The purpose of this study is to investigate the effects of atomized inhalation of Sapylin versus Dexamethasone on the incidence and severity of RIOM, and to further evaluate the safety and effectiveness of aerosol inhalation of Sapylin and Dexamethasone in NPC patients receiving CCRT. This study will provide NPC specialists and patients with an efficient and low-toxicity method to reduce the occurrence and severity of RIOM and improve the efficacy of CCRT.

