## **3. Research Protocol**

### **3.1 Study Design Type**

Non-inferiority, parallel-design, randomized controlled clinical study.

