### **3.3 Inclusion and Exclusion Criteria and Sample Size Estimation**

(1) Patient Selection: Meeting the diagnostic criteria for NPC; patients who have not yet received concurrent chemoradiotherapy; meeting the case inclusion and exclusion criteria; patients voluntarily joining this clinical trial and signing the informed consent form.

(2) Sample Size Estimation: The Delphi method is used to determine the non-inferiority margin of the observation endpoint. After consulting senior oncology practitioners, we defined an 8% reduction in the incidence of RIOM as a clinically acceptable non-margin of error. Under the conditions of test level  $\alpha=0.05$  and test efficacy  $1-\beta=0.9$ , the proportion of cases in the two groups is 1:1. Using the module of non-destructiveness Tests for Two Proportions in PASS 15.0 statistical analysis software, we determined that a sample size of 81 was required per group. Considering a 10% loss to follow-up rate, we estimated that 90 cases would be required in each group, for a total of 180 cases.

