### (2) Statistical Analysis

① General Principles: One-sided tests will be used for superiority tests, while two-sided tests will be used for other statistical tests. Quantitative indicators will be described using the number of cases, mean, standard deviation, median, minimum, and maximum. Categorical indicators will be described using the number of cases and percentages. All statistical analyses will be conducted using SPSS 26.0 statistical software.

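### The primary endpoint carries only a non-inferiority hypothesis, with an opinion-based margin and no documented comparator effect, while the stated goal is to reduce RIOM

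*Protocol*

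**What the plan says.** Protocol II.3.1 gives the design as "Non-inferiority, parallel-design, randomized controlled clinical study", and the title and part VIII repeat it. On the margin, II.3.3 (2) says "The Delphi method is used to determine the non-inferiority margin of the observation endpoint", and then "we defined an 8% reduction in the incidence of RIOM as a clinically acceptable non-margin of error". It adds alpha 0.05, power 0.9 and 1:1 allocation, arrives at 81 per group, and raises this to 90 for 10% loss. It states no event rates.

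The purpose in II.2.1 is to give specialists and patients a "method to reduce the occurrence and severity of RIOM". The same wish to lower RIOM appears in II.1.2 and in part IV.1.

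On the comparator, I.1 Background says "Epidermal Growth Factor (EGF) and corticosteroids are recommended". Section I.2 (2) says of the guidelines and consensus "nor do they recommend the local prophylactic use of antibiotics and hormones". Under II.3.5 dexamethasone is nebulised from Day 1, and inclusion criterion (4) in part III requires normal oral mucosa before treatment.

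The general principles in II.7 (2) say "One-sided tests will be used for superiority tests, while two-sided tests will be used for other statistical tests". They assign a superiority test to no endpoint and do not mention non-inferiority.

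**The concern.** A non-inferiority result says that the new treatment is not worse than the comparator by more than the margin. It becomes evidence that the new treatment works only if the comparator is known to work by more than the margin. Here that link is missing. The margin comes from opinion, and the protocol gives no estimate of what preventive nebulised dexamethasone does to RIOM incidence against nothing.

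The goal of lowering RIOM is a superiority question, but the only hypothesis tied to the primary endpoint is non-inferiority. A trial that met its margin could be reported as having reached that goal when no reduction had been shown. If Sapylin really is better, a superiority claim that was not stated beforehand would look post hoc.

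**Working it through.** **Inputs.** Margin 8%, read as 8 percentage points; alpha 0.05; power 0.90; 81 per group (II.3.3). Rates come from the 32-patient retrospective series in part VIII, because II.3.3 gives none: RIOM 43.75% with Sapylin (7/16) and 68.75% with dexamethasone (11/16).

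**Step 1: reproduce 81.**

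*As non-inferiority at equal rates p:* n = 2p(1-p)(z_alpha + z_beta)^2 / 0.08^2. With p = 0.6875, 2p(1-p) = 0.4297.
- One-sided 0.05: 0.4297 x 8.564 / 0.0064 = 575 per group.
- One-sided 0.025: 0.4297 x 10.507 / 0.0064 = 706 per group.

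At an assumed 80% in both arms the figures are 429 and 526. At the pilot rates (68.75% vs 43.75%) they are 37 and 45. Equal rates give 81 only near 97%.

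*As two-sided superiority at the pilot rates*, pooled variance under the null, mean rate 0.5625: n = (1.960 x sqrt(2 x 0.5625 x 0.4375) + 1.2816 x sqrt(0.6875 x 0.3125 + 0.4375 x 0.5625))^2 / 0.25^2 = (1.3750 + 0.8701)^2 / 0.0625 = 80.6, so **81**. Then 81/0.9 = 90. Both stated figures are matched.

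**Step 2: power of 81 per group for non-inferiority at equal rates of 68.75%.** SE = sqrt(0.4297/81) = 0.0728.
- One-sided 0.05: Phi(0.08/0.0728 - 1.645) = 29%.
- One-sided 0.025: Phi(0.08/0.0728 - 1.960) = 19%.

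**Step 3: which observed results pass which test.** Let d be the observed difference, Sapylin minus dexamethasone, with control at 68.75% and SE = sqrt((pc qc + pt qt)/81). The upper limit of the two-sided 95% CI is d + 1.96 SE.
- Upper limit = +8 points: d = -6.6 points (pt = 62.1%, SE 7.45 points; -6.6 + 14.6 = 8.0).
- Upper limit = 0: d = -14.8 points (pt = 53.9%, SE 7.56 points; -14.8 + 14.8 = 0).

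Differences between about -6.6 and -14.8 points meet non-inferiority without excluding zero. With one-sided 0.05 limits the corresponding values are -4.2 and -12.4 points.

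**Step 4: power of a superiority step at 81 per group** (control 68.75%, two-sided 0.05, unpooled SE): 91%, 75%, 51% and 26% for true reductions of 25, 20, 15 and 10 points.

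**Step 5: what is known of the comparator.** For local corticosteroids, I.1 and I.2 (2) report relief of oedema, inflammation and symptoms. For systemic use they report no decrease in RIOM incidence or severity. The retrospective series has no untreated arm. An effect of local dexamethasone on incidence cannot be taken from any of these.

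**The case against.** Several points on the other side stand.

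- A reader might infer that non-inferiority is the only test foreseen. The text does not support that. The general principles in II.7 (2) provide for one-sided superiority tests, and the statistical section sets out no efficacy test of either kind. What can be said is that non-inferiority is the only hypothesis tied to the primary endpoint.
- A reader might infer that a positive trial could never support a reduction. That is too strong: an interval excluding zero would support a reduction against dexamethasone.
- A reader might infer that the protocol calls its comparator not recommended. It says so of local prophylactic hormones, which probably but not explicitly means corticosteroids. Elsewhere it says corticosteroids are recommended, and I.2 (2) also lists them among agents in use for prevention and treatment. The supportable point is a contradiction.
- A reader might infer that success would admit results 8 points worse (76.75% against 68.75%). That is the null boundary. By Step 3, passing needs Sapylin to be observed about 4.2 to 6.6 points better. A drug truly 8 points worse passes with probability 5% or 2.5%.
- Non-inferiority has a rationale here: I.1 links long-term local corticosteroids to fungal infection, so similar efficacy with less toxicity is a coherent aim.
- A test sequence is often left to a statistical analysis plan, which is not shown and may contain one.

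The last point limits the criticism but does not remove it. The mismatch between hypothesis and goal, the corticosteroid contradiction, and a sample size that fits a different hypothesis from the stated one are all in the protocol itself.

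**Conclusion.** The point holds in this limited form: the hypothesis attached to the primary endpoint does not answer the stated goal, and the protocol does not establish the comparator effect that would let non-inferiority stand in for efficacy. The size is a band of observed differences, about -6.6 to -14.8 points, that would be a formal success without a demonstrated reduction. The stated 81 per group serves superiority at the pilot rates (90.1% power by the formula in Step 1) and leaves non-inferiority at equal rates with 19% to 29%.

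This rests on reading 8% as an absolute difference, on a control rate of 68.75% taken from 16 patients, on normal approximations, and on 81 evaluable patients per group. It is a matter that should be corrected; it does not invalidate the trial.

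**What to change.** Before comparative data are seen, amend the protocol as follows.

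1. In II.7 (2), state a fixed sequence for RIOM incidence. First, non-inferiority: upper limit of the two-sided 95% CI for Sapylin minus dexamethasone below +8 points. Then, only if met, superiority: upper limit of the same interval below 0.
2. Change the one-sided rule for superiority in II.7 (2) to match that interval.
3. State that only the second step supports a claim that Sapylin reduces RIOM compared with dexamethasone. The first step alone supports only that it is not more than 8 points worse than dexamethasone, and says nothing about efficacy over no prophylaxis.
4. Reconcile I.1 and I.2 (2) on corticosteroids.
5. In II.3.3 and the matching text in part III.5, state which hypothesis 81 per group serves, with the rates and sidedness used, and report the power for the other hypothesis.

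The cost is wording. Because the order is fixed, no alpha and no patients are spent, and no treatment changes. The price is a narrower claim if only non-inferiority is met, and a stated non-inferiority power well below 90% if the true rates are equal. The sequence does not supply the missing evidence behind the margin; it limits what may be concluded without it.
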